### 8.2.3 Brief Physical Examination

The following sites/systems will at least be included in the brief physical examination that will be performed at the visits specified in [Table 1](#) (Cohort 1) and [Table 2](#) (Cohort 2):

- General appearance

- Dermatological (except FFA)
- Respiratory
- Cardiovascular
- Abdominal

If deemed appropriate by the investigator based on the subject's condition, a complete physical examination as described in Section [8.2.2](#) can be performed instead of a brief examination.

Information for all physical examinations must be included in the source document. If deemed appropriate by the investigator, clinically significant findings in the physical examination will exclude a subject from trial participation. For Cohort 1 only, any significant change will be reported as an AE in the source document and eCRF.

#### 8.2.4 Clinical Laboratory Tests

For subject in Cohort 1 only, laboratory tests will be performed at the visits specified in [Table 1](#). The tests will include hematology with differential, a standard chemistry panel (chemistry includes liver function tests), TSH with reflex free T4 (screening), serum pregnancy test (screening) or urine pregnancy test (at other visits) for women of childbearing potential (WOCBP). The specific tests in these panels are listed in [Table 7](#).

**Table 7: Clinical Laboratory Testing (Cohort 1)**

Laboratory Testing	Tests Included
Hematology	HCT, Hgb, MCH, MCHC, MCV, MPV, PLT, RBC, WBC, and differentials (neutrophils, lymphocytes, monocytes, eosinophils, and basophils relative and absolute)
Biochemistry	Albumin, alkaline phosphatase, ALT, AST, chloride, creatinine (enzymatic), GGT, glucose random, LDH, potassium, sodium, total bilirubin, triglycerides, urea (BUN), uric acid
Urine pregnancy test	For female subjects of childbearing potential (at each visit, except screening)
Laboratory tests required at screening only	β-hCG for female subjects of childbearing potential Serology (HBV (HBsAg, anti-HBc), HCV, HIV) TSH with reflex free T4 (ie, free T4 will be performed only if TSH value is abnormal)

Abbreviations: ALT, alanine aminotransferase; anti-HBc, antibody to hepatitis B core antigen; AST, aspartate aminotransferase; β-hCG, β-human chorionic gonadotropin; BUN, blood urea nitrogen; GGT, gamma-glutamyl-transferase; HBsAg, hepatitis B surface antigens; HBV, hepatitis B virus; HCT, hematocrit; HCV, hepatitis C virus; Hgb, hemoglobin; HIV, human immunodeficiency virus; LDH, lactate dehydrogenase; MCH, mean corpuscular hemoglobin; MCHC, mean corpuscular hemoglobin concentration; MCV, mean corpuscular volume; MPV, mean platelet volume; PLT, platelets; RBC, red blood cell (count); TSH, thyroid-stimulating hormone; WBC, white blood cell (count).

In case of a screening laboratory value abnormality, the test can be repeated once within the original screening time window, if the investigator believes there is a reasonable possibility that the subject would be eligible if re-tested.

If deemed appropriate by the investigator, clinically significant findings in clinical laboratory testing will exclude a subject from trial participation. Any clinically significant value will be reported as an AE.

### **8.2.5 Electrocardiogram**

For subjects in Cohort 1, a twelve-lead ECG will be performed as a safety assessment at the visit specified in [Table 1](#). Clinically significant findings in the ECG should exclude a subject from study participation (as deemed appropriate by the investigator). Any clinically significant value will be reported as an AE.

### **8.2.6 Local Tolerability Assessments**

For subjects in Cohort 1, subject local tolerability assessments will be performed at the visits specified in [Table 1](#). On Day 1 and Week 12, the assessment will be performed approximately 30 minutes after the IMP application at the site with a recall period of 30 minutes. At other visits, the subject's local tolerability assessment will be done before the IMP application with a recall period of 7 days (worst over the last 7 days). The subject will evaluate stinging/burning at the application site using the scale described in [Table 8](#).

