
After the vehicle-controlled treatment period, subjects will continue into the OLE and will apply delgocitinib cream 20 mg/g BID for 12 weeks.
 

• Cohort 2

- No investigational product will be administered in Cohort 2.

		

Objectives:
		

Primary:
 
The primary objective is:
 

• To assess molecular signature changes following topical application of delgocitinib cream 20 mg/g in subjects with FFA.

		

Secondary:
 
The secondary objective is:
 

• To evaluate the safety and tolerability of delgocitinib cream 20 mg/g following topical application in subjects with FFA during the vehicle-controlled treatment period.

		

Exploratory:
 
The exploratory objectives are:
 

• To evaluate the safety and tolerability of delgocitinib cream 20 mg/g during the OLE.

• To evaluate the preliminary efficacy of delgocitinib cream 20 mg/g following topical application in subjects with FFA.

		

Endpoints:
		

Primary Endpoint:
 

• Change in expression of chemokine (C-X-C motif) ligand 9 (CXCL9), chemokine (C-X-C motif) ligand 10 (CXCL10), and interferon (IFN)-<math>\gamma</math> from baseline to Week 12.

		

Secondary Endpoint:
 

• Number of treatment-emergent adverse events (TEAEs) from baseline to Week 12.

		

Exploratory Endpoints:
		

Exploratory safety endpoint:
 

• Number of TEAEs during the OLE (up to Week 26)

		

Exploratory efficacy endpoints during the vehicle-controlled treatment period:
 

• Change in Lichen Planopilaris Activity Index (LPPAI) score from baseline to Weeks 4, 8, and 12.

• Change in Frontal Fibrosing Alopecia Severity Score (FFASS) from baseline to Weeks 4, 8, and 12.

• Change in target area perifollicular erythema score from baseline to Weeks 4, 8, and 12.

• Change in target area perifollicular scale score from baseline to Weeks 4, 8, and 12.

• Change in pruritus Numerical Rating Scale (NRS) score from baseline to Days 2, 3, 4, 5, 6, 7, 8, and Weeks 4, 8, and 12.

		

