## 1.3 Schedule of Events

The screening evaluation will only be performed after the subject has agreed to participate and has signed and dated the ICF. No treatment or trial-related procedures will be initiated before the informed consent is signed. The Day 1 visit must be performed, at the latest, 30 days after the screening visit. For Cohort 2 only (healthy subjects), the sample collections on Day 1 can be performed on the same day as the screening visit or on separate visits as per the schedule of events, at the investigator's discretion.

The screening evaluation will be performed according to the inclusion and exclusion criteria. If the subject fulfills all inclusion criteria and no exclusion criteria, he or she may be included in the trial.

**Table 1** and **Table 2** provide a description of the procedures to be performed at each visit for Cohort 1 and Cohort 2, respectively.

Unless specified otherwise, the trial assessments scheduled during the trial visits must be performed before the IMP application for subjects in Cohort 1. If assessments are scheduled for the same nominal time, then the assessments should occur in the following order:

- Patient-reported outcomes
- Investigator assessments
- Vital signs
- Medical photographs
- Collection of skin samples

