Abbreviations: anti-HBc, antibody to hepatitis B core antigen; BID, twice daily; ET, early termination; FFA, frontal fibrosing alopecia; FFASS, Frontal Fibrosing Alopecia Severity Score; HBV, hepatitis B virus; HBsAg, hepatitis B surface antigen; HCV, hepatitis C virus; HIV, human immunodeficiency virus; IMP, investigational medicinal product; LPPAI, lichen planopilaris activity index; NRS, Numerical Rating Scale; OLE, open-label extension; TSH, thyroid-stimulating hormone; V, visit.

a For female subjects of childbearing potential, serum pregnancy test at screening and urine pregnancy test at other specified visits.

b Including height and weight. Height will be measured only at screening.

c The lesional target area should be treated with the IMP and should be approximately 3 cm x 6 cm (or equivalent). However, a smaller lesional target area can be selected if tape stripping is performed from the same area where trichoscopy/hair counts is performed or if sample is collected adjacent/close to the lesional target area (refer to Section 8.3.2 for details). If needed, two small lesional target areas (totalling approximately the same size) could be selected to allow for skin samples collection.

d Subjects will complete their NRS at home on a daily basis starting approximately 7 days prior to Day 1 and up to Day 8. On Day 1, the NRS will be completed at the site prior to the first IMP application. After Day 8, the NRS will be completed at the site at the specified visits only.

e Hair line measurements of lateral canthus (right and left) to hairline, lower glabellar crease to hair line, top of frontalis muscle to hair line, and mid brow to hair line (right and left).

f Medical photographs of the target area and the entire scalp (including the frontal hair line and right and left hair line areas).

g The morning application will be on site on visit days. Other IMP applications will be done at home. The first application of the OLE (delgocitinib cream 20 mg/g) is on the morning of Week 12, after all efficacy assessments and skin sample collections are completed. The last application of the OLE is the evening prior to the Week 24 visit. No IMP application will be done on the day of the Week 24 visit.

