h Local tolerability assessments will be done by subjects. On Day 1 and Week 12, the local tolerability assessment will be done approximately 30 minutes after the IMP application at the site, with a recall period of 30 minutes. At other visits, the subject's local tolerability assessment will be done before the IMP application with a recall period of 7 days (worst over the last 7 days).

Trial Visits	Screening	Treatment Period							Follow-Up	ET		
		Vehicle-Controlled				OLE						
		Day 1	Week 4	Week 8	Week 12	Week 16	Week 20	Week 24				
	V1	V2	V3	V4	V5	V6	V7	V8	V9	-		
Window (days)	-30 to -1	-	±2	±2	±2	±4	±4	±4	±4	-		

i On Day 1, 2 skin biopsies (4-mm) will be collected prior to the first IMP application (1 from a lesional hair follicle within the target area and 1 from a non lesional hair follicle [eg, on the occipital scalp]). On Week 12, 1 skin biopsy (4-mm) will be collected from a hair follicle within the lesional target area (outside the scar of previous biopsies).

j Within 10 to 14 days after biopsy collection, suture may be removed, if needed. An additional visit(s) may be necessary for suture removal only, if suture removal is needed after Day 1 and/or Week 12.

k On Day 1, optional skin tape strips will be collected prior to the first IMP application from lesional skin and from non lesional skin (eg, on the occipital scalp). The lesional skin tape strip should ideally be collected from the target area but can also be collected adjacent/close to the target area, as long as it includes a portion of lesional skin and is treated with the IMP. On Week 12, skin strips will be collected at the same location of the lesional skin. Every effort should be made to collect tape strip samples in all subjects however, adhesive tape strip collection is optional and will be collected per investigator judgement (based on available skin area on the scalp).

l On Day 1, skin swab for microbiome analysis will be collected prior to the first IMP application (1 from the target area [lesional skin] and 1 from an uninvolved occipital scalp area). On Week 12, skin microbiome will be collected at the same location of the lesional skin of the target area.

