### 3 OBJECTIVES AND ENDPOINTS

OBJECTIVES	ENDPOINTS
Primary	
To assess molecular signature changes following topical application of delgocitinib cream 20 mg/g in subjects with FFA	Primary endpoint: 

Change in expression of CXCL9, CXCL10, and IFN-<math>\gamma</math> from baseline to Week 12.

Secondary	Safety endpoint during the vehicle-controlled treatment period: 

Number of TEAEs from baseline to Week 12.

Exploratory	Exploratory safety endpoint: 

Number of TEAEs during the OLE (up to Week 26)

 Exploratory efficacy endpoints during the vehicle-controlled treatment period: 

Change in LPPAI score from baseline to Weeks 4, 8, and 12.

Change in FFASS score from baseline to Weeks 4, 8, and 12.

Change in target area perifollicular erythema score from baseline to Weeks 4, 8, and 12.

Change in target area perifollicular scale score from baseline to Weeks 4, 8, and 12.

Change in pruritus NRS score from baseline to Days 2, 3, 4, 5, 6, 7, 8, and Weeks 4, 8, and 12.

Change in burning sensation NRS score from baseline to Days 2, 3, 4, 5, 6, 7, 8, and Weeks 4, 8, and 12.

Change in pain NRS score from baseline to Days 2, 3, 4, 5, 6, 7, 8, and Weeks 4, 8, and 12.

Proportion of subjects with a 3-point reduction* in pruritus NRS score from baseline to Days 2, 3, 4, 5, 6, 7, 8, and Weeks 4, 8, and 12.

Proportion of subjects with a 4-point reduction* in pruritus NRS score from baseline to Days 2, 3, 4, 5, 6, 7, 8, and Weeks 4, 8, and 12.

OBJECTIVES	ENDPOINTS
	

• Proportion of subjects with a 3-point reduction* in burning sensation NRS score from baseline to Days 2, 3, 4, 5, 6, 7, 8, and Weeks 4, 8, and 12.

• Proportion of subjects with a 4-point reduction* in burning sensation NRS score from baseline to Days 2, 3, 4, 5, 6, 7, 8, and Weeks 4, 8, and 12.

• Proportion of subjects with a 3-point reduction* in pain NRS score from baseline to Days 2, 3, 4, 5, 6, 7, 8, and Weeks 4, 8, and 12.

• Proportion of subjects with a 4-point reduction* in pain NRS score from baseline to Days 2, 3, 4, 5, 6, 7, 8, and Weeks 4, 8, and 12.

• Change in target area hair counts/trichoscopy via fotofinder trichovision from baseline to Week 12.

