#### 8.5.5 Time Period and Frequency for Event Assessment and Follow-Up

The occurrence of an AE or SAE may come to the attention of trial personnel during trial visits and interviews of a trial subject presenting for medical care, or upon review by a trial monitor.

At all visits, the subject will be asked a non-leading question by the investigator about AEs, eg.: 'How have you felt since I saw you last?'. It is important that the investigator also observes the subject for any changes not reported by the subject and records these changes.

All AEs, including cutaneous and systemic reactions, will be captured on the appropriate eCRF. Information to be collected includes event description, date of onset, clinician's assessment of severity, relationship to IMP (assessed only by those with the training and authority to make a diagnosis, ie, the investigator), and date of resolution/stabilization of the event. All AEs occurring while on trial must be documented appropriately regardless of relationship.

Trial site personnel will note the occurrence and nature of each subject's medical condition(s) present prior to the informed consent signature in the appropriate section of the source document and eCRF. During the trial, site personnel will note any change in the condition(s) and the occurrence and nature of any AE.

Any medical condition that is present prior to informed consent signature will be considered as part of medical history and not reported as an AE. However, if the trial subject's condition deteriorates after the consent signature, it will be recorded as an AE.

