### Burning Sensation NRS

On scale from 0 (“no burning sensation”) to 10 (“worst imaginable burning sensation”), how was your worst burning sensation due to your frontal fibrosing alopecia in the past 24 hours? Please select one number.

Numeric Rating Scale										
 0	 1	 2	 3	 4	 5	 6	 7	 8	 9	 10
No burning sensation						Worst imaginable burning sensation				

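### Completers have no stinging/burning grade on randomised treatment after Week 8, because the only Week 12 grade follows the first open-label dose; Sections 8.2.6 and 9.3.4.1 also disagree on AE recording.

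*Combined protocol and SAP*

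**What the plan says.** The Synopsis (Section 1.1) sets a single secondary objective, worded thus: "To evaluate the safety and tolerability of delgocitinib cream 20 mg/g following topical application in subjects with FFA during the vehicle-controlled treatment period". Its endpoint in Section 3 is "Number of TEAEs from baseline to Week 12".

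Local tolerability is the subject's own 0 to 3 grade of stinging/burning at the application site (Section 8.2.6, Table 8). Table 1 schedules it at Day 1, Weeks 4, 8, 12, 16, 20 and 24, and at early termination (ET). Week 12 carries a single mark, under the vehicle-controlled columns.

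Two timings apply:

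- **Day 1 and Week 12:** "On Day 1 and Week 12, the assessment will be performed approximately 30 minutes after the IMP application at the site", with a 30-minute recall (Section 8.2.6; Table 1, footnote h, agrees).
- **All other visits:** the grade "will be done before the IMP application with a recall period of 7 days (worst over the last 7 days", as footnote h puts it.

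Footnote g identifies the product applied at Week 12: "The first application of the OLE (delgocitinib cream 20 mg/g) is on the morning of Week 12". Section 4.1 sends every completer of the vehicle-controlled period into the open-label extension (OLE).

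On AEs, the text under Table 8 makes reporting of the subject's assessment optional, at the investigator's discretion. Section 9.3.4.1 says that new findings on local tolerability assessments will be recorded as AEs.

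**The concern.** The grade that Table 1 places at the end of the vehicle-controlled period does not describe that period. It describes the first half hour of open-label delgocitinib in both arms. No vehicle-arm grade exists for the last four weeks on vehicle, and no between-arm comparison of graded stinging/burning is possible at the end of randomised treatment. A table that followed the Table 1 columns and showed Week 12 by randomised arm would also attribute a reaction to delgocitinib to vehicle.

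The AE wording is a second, separate matter. A newly reported grade falls under both sentences, one permissive and one mandatory. The secondary endpoint is a count of TEAEs, so the same report could be counted or not, depending on which sentence the site follows.

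**Working it through.** The plan gives no figure to reproduce here. The check is a cross-reading of the schedule, followed by simple counts.

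**Which product each grade describes, for a completer**

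| Visit | Timing and recall | Product described |
|---|---|---|
| Day 1 | about 30 min after dose, 30-min recall | randomised |
| Week 4 | before dose, 7-day recall | randomised |
| Week 8 | before dose, 7-day recall | randomised |
| Week 12 | about 30 min after dose, 30-min recall | open-label delgocitinib, both arms |
| Week 16 | before dose, 7-day recall | open-label delgocitinib |

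Grades on randomised treatment: Day 1 + Week 4 + Week 8 = 3. A pre-dose Week 12 grade would make 4, and would raise the number of 7-day recalls from 2 to 3.

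**Length of the gap** (Day 1 = 1, Week 8 = Day 57, Week 12 = Day 85, Week 16 = Day 113; windows from Table 1)

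- Week 8 to Week 12: 85 − 57 = 28 days. With the ±2-day windows the range is 83 − 59 = 24 to 87 − 55 = 32 days.
- Share of the randomised period: 28/84 = 33.3%.
- Days covered by 7-day recall: 2 × 7 = 14 of 84 (16.7%) now; 3 × 7 = 21 of 84 (25.0%) with a pre-dose Week 12 grade.
- Of the 28 days, 7 would be recovered and 28 − 7 = 21 would stay ungraded, as between the other visits.

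**Can Week 16 reach back?** The earliest Week 16 visit is Day 113 − 4 = 109, and its recall starts on Day 109 − 7 = 102. The latest Week 12 visit is Day 85 + 2 = 87. It cannot.

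**Does another item fill the gap?** The burning NRS asks "how was your worst burning sensation due to your frontal fibrosing alopecia in the past 24 hours". That is a disease symptom over one day, not a reaction at the application site. AE questioning does continue: "At all visits, the subject will be asked a non-leading question by the investigator about AEs". Table 1 also has a complete physical examination at Week 12. Subjects who stop early and attend the ET visit give a 7-day grade there, so the gap concerns completers only.

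**How much the recovered reading could show.** About 30 subjects randomised 1:1 is about 15 per arm. If no subject in an arm reported stinging, the exact one-sided 95% upper limit on the true rate is 1 − 0.05^(1/n):

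- n = 15: 1 − 0.05^(1/15) = 0.181, or 18%.
- n = 12 (assuming 20% do not complete; 15 × 0.8 = 12): 1 − 0.05^(1/12) = 0.221, or 22%.

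These limits show only that the reading would be descriptive. They would apply equally to Weeks 4 and 8 at the same n.

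**The AE sentences side by side.** In Section 9.3.4.1 the clinical-significance qualifier precedes laboratory and vital-sign changes; local tolerability has its own trigger, a new finding. A first report of grade 1, which Table 8 describes as hardly troublesome, is optional under Section 8.2.6 and mandatory under Section 9.3.4.1. New findings are a narrower class than all reported grades, but they lie wholly inside the discretion that Section 8.2.6 grants. The two rules therefore collide for those reports.

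**The case against.** The Week 12 timing looks deliberate. The version history cites an FDA recommendation that subjects starting delgocitinib be monitored alike whether they start in the OLE or in the initial period, and it lists Section 8.2.6 among the changed sections. A 30-minute reading after the first delgocitinib dose mirrors Day 1. This stands: the post-dose reading is useful and should stay. It explains why that reading exists, not why there is no pre-dose one.

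No stated analysis uses the grade. The secondary endpoint is the TEAE count, and Section 9.3.4.1 plans tables by treatment and visit for laboratory results and vital signs, not for this grade. This also stands and limits the importance of the point. The safety details deferred to a separate SAP (Section 9.3.1) may settle the period to which the Week 12 grade belongs, but no SAP can recover a reading that was not collected.

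Existing coverage is not negligible. The Week 12 burning NRS is completed before application, covers the last 24 hours, concerns skin to which the cream is applied, and is compared between arms. It remains worded as burning due to the disease, so it is only a partial stand-in.

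On AE recording, the trial is single-site and the vehicle-controlled period is double-blind. Whichever sentence the site follows should apply to both arms alike, so the risk is to the absolute TEAE count rather than to the comparison. That is fair, and no between-arm bias is claimed here.

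**Conclusion.** Both parts hold, and both are minor. Completers have 3 grades on randomised treatment where 4 are readily obtainable, and 0 of about 15 vehicle subjects have a Week 12 grade on vehicle. The cost is one descriptive tolerability reading at the end of the period named in the secondary objective; no endpoint or test is lost. The day counts rest on nominal visit days and the Table 1 windows, and the 22% limit rests on an assumed 20% non-completion.

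The AE-recording conflict is an internal inconsistency that bears on the secondary endpoint. Its effect on the TEAE count cannot be sized from the documents.

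**What to change.** 1. At Week 12, ask the existing stinging/burning item before application, with the 7-day recall used at Weeks 4 and 8, and summarise it with the vehicle-controlled period.
2. Keep the 30-minute post-dose reading and summarise it as OLE data.
3. Reconcile Sections 8.2.6 and 9.3.4.1 to one rule for recording tolerability findings as AEs. Which rule to adopt is for the sponsor to decide.

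The cost is one extra question at an existing visit, a minor form change and one wording edit. The question fits the visit flow: Section 1.3 already puts patient-reported outcomes first and, unless otherwise specified, "the trial assessments scheduled during the trial visits must be performed before the IMP application for subjects in Cohort 1". Section 8.2.6 is such a stated exception for Day 1 and Week 12, so the present timing does not contradict Section 1.3. The downside is that the item is asked twice at Week 12, so the form must label the two recall periods clearly.
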